8.4 Study Treatment Assignment

Patients will be assigned to a dose level in the order of study entry.

8.5 Treatment Accountability and Compliance

All drug supplies will be provided by the Sponsor. Administration of study drugs will be supervised by study personnel to ensure compliance.

8.6 Prior and Concomitant Illnesses and Medications

8.6.1 Prior and Concomitant Illnesses

Investigators should document all prior significant illnesses that the patient has experienced prior to screening. Additional illnesses present at the time when informed consent is given and up to the time of first dosing are to be regarded as concomitant illnesses. Illnesses first occurring or detected during the study and/or worsening of a concomitant illness during the study are to be documented as AEs on the eCRF.

8.6.2 Prior and Concomitant Medications

All medications and other treatments taken by the patient prior to the start of the study at screening and treatments initiated during the study, must be recorded on the eCRF. The entry must include the dose, regimen, route, indication, and dates of use.

After the baseline visit, medication to treat minor illness(es) are generally permitted, including:

- Use of localized palliative radiation for pre-existing lesions to control pain, at the discretion of the physician.
- Corticosteroids use: topical, inhaled, ophthalmologic, intra-articular, or intranasal corticosteroids; systemic steroids at physiologic doses not to exceed 10 mg/day of prednisone or equivalent. For management of side effects including nausea or infusion reactions, intermittent prophylactic or therapeutic use of glucocorticoids is allowed at doses required for medical therapy administered according to institutional standard of care and at the Investigator's discretion.

8.6.3 Prohibited Medications

If there is a clinical indication for the use of one of these prohibited medications, then discontinuation from the study drug may be required.

- Anti-neoplastic therapy, whether approved or experimental, including but are not limited to: chemotherapy, immunotherapy, surgery, radiotherapy are not allowed with OBI-888. **NOTE:** Use of localized palliative radiation for pre-existing lesions to control pain may be allowed at the discretion of the physician.
- Immunosuppressive therapy (e.g., cyclosporine, rapamycin, tacrolimus, cyclophosphamide, methotrexate, etc.).
- Systemic steroids of >10 mg/day prednisone or equivalent
- Any other concurrent investigational therapy, regardless of indication.

9 Study Procedures

Table 9-1 outlines the timing of procedures, and assessments to be performed throughout the study.

The PK sampling schedule is outlined in Table 9-2 (Part A – Dose Escalation) and Table 9-3 (Part B - Expansion).

9.1 Subject Informed Consent

Prior to performing any study-related procedures, the Investigator (or his/her designated staff member) will obtain written informed consent from the patient.

9.2 Procedures by Study Period

Assessments and study procedures are to be performed as outlined in The Schedule of Assessments, Table 9-1. The PK, ADA, Biomarker, and Glycan Sampling Schedule is provided in Table 9-2 (Part A – Dose Escalation) and Table 9-3 (Part B - Expansion).

The Investigator may at his/her discretion arrange for a patient to have an unscheduled assessment, especially in the case of AEs that require follow-up or an AE considered by the Investigator to be possibly related to the use of study drug. The unscheduled visit page on the eCRF must be completed. Additional visits to follow-up positive ADA may happen after end of study (Table 9-1).

Table 9-1Schedule of Assessments

| Study Procedure | Screening Visit** | Treatment Period | | | | | | |
|--|-------------------|------------------|---|--------|---|---|---------|--|
| Cycle (C) # | - | Cycle 1 | | | | Cycle 2-13 | | |
| Cycle # and Day | | C1D1 | 1D1 C1D8 C1D15 C1D22 | | C1D22 | | | |
| Window period (days) | -28 to -1 days | -1* | ±1 | ±3 | ±3 | ± 3 days | ±7 days | |
| Informed consent ^a | Х | | | | | | | |
| Demographics | Х | | | | | | | |
| Eligibility screening | Х | Х | | | | | | |
| Medical history ^b | X | Х | | | | | | |
| Physical examination ^c | Х | Х | Х | Х | Х | D1 of each Cycle | X | |
| Height, weight ^d | Х | X X X X | | | | D1 of each Cycle | X | |
| Vital signs ^e | X | X X X X | | | Х | D1, D8, D15, D22 of each Cycle | Х | |
| ECOG ^f | Х | | | | | D1 of each Cycle | Х | |
| 12-lead ECG ^g | Х | Х | | | | | | |
| Pregnancy testing ^h | Х | | | | | | X | |
| Tumor biopsy ⁱ | X** | | | | | | | |
| Hematology and Biochemistry ^j | Х | Х | | | | D1 of each Cycle | Х | |
| Coagulation and Urinalysis ^k | Х | Х | | | | | | |
| Drug administration ¹ | | Х | Х | Х | Х | D1, D8, D15, D22 of each 28 day cycle | | |
| Pharmacokinetic sample ^m | | | | See fo | otnote m | and Table 9-2 (Part A) and Table 9-3 (Part B) | | |
| Immunogenicity (ADA) ⁿ | | | | See fo | otnote n | and Table 9-2 (Part A) and Table 9-3 (Part B) | | |
| Biomarkers ^o | Х | | | See fo | otnote o | and Table 9-2 (Part A) and Table 9-3 (Part B) | | |
| Radiology evaluations (CT or MRI) ^p | X | | Q8wk (±1 wk) for the first then Q12wk (±1 wk) th | | Q8wk (±1 wk) for the first 6 months, then Q12wk (±1 wk) thereafter | X | | |
| Concomitant medications | • | • | • | • | • | | | |
| Adverse events | | | | | | | | |

EOS/ET - End of Study/Early Termination. EoS Visit is the safety follow-up visit, conducted 28±7 days after the last OBI-888 dose. ET visit lab assessments will be conducted for subjects discontinuing study treatment, if last available tests are before 2 weeks.

*The -1 day window (1 day prior) for C1D1 is for safety laboratory assessments. Blood can be drawn 1 day prior to initiation of study drug infusion on C1D1. Safety laboratory results should be available and reviewed by the Investigator prior to the OBI-888 administration.

** All patients are required to provide a tumor biopsy sample, unstained slides (preferred) or a formalin fixed paraffin embedded (FFPE) tissue block at the initiation of screening visit for screening of Globo H overexpression and confirmation for eligibility of subjects for Part B. Patients with a confirmed and documented Globo H H-score of ≥ 100 are eligible for the study, and will subsequently enter the 28-day screening period to complete the remaining screening procedures.

Footnotes:

- a. Informed consent to be obtained before any other study procedures are performed.
- b. Medical history to include previous cancer therapies, cancer history, and past and ongoing concomitant illnesses.
- c. A complete physical examination is required at screening and at discontinuation. Directed physical examinations may be limited to problem focused review of symptoms and major organ systems at D1 of each cycle and prior to infusion.
- d. Height to be obtained at screening only. Weight obtained at D1 of each cycle, prior to infusion. If during treatment a patient's body weight changes by >10% from the baseline value, the OBI-888 dose should be adjusted.
- e. Vital signs include temperature, blood pressure and pulse (at supine position) prior to every infusion. Temperature measurement will be obtained as clinically indicated.
- f. ECOG performance status: at baseline, C2D1 and end of study/early termination.
- g. 12-lead ECG: at screening and pre and post infusion at C1D1 (within one hour after end of infusion).
- h. Pregnancy testing should be performed in females of childbearing potential only. A urine or serum pregnancy test is acceptable.
- i. Tumor biopsy samples are mandatory at screening visit. Fresh (preferred) tissue or archival tissue is acceptable. A minimum of 3 slides are required for the central laboratory Globo H assay for determination of eligibility. Up to 12 unstained additional slides should be provided, depending upon availability, for the protocol-defined exploratory studies.
- j. Hematology and Serum chemistry (Laboratory Assessments: Table 12-1). Blood draw is prior to OBI-888 infusion.

Hematology: hematocrit, hemoglobin, red blood cell (RBC) count, white blood count (WBC), absolute counts of leukocytes, neutrophils, lymphocytes, monocytes, eosinophils, basophils, and platelet count.

Serum chemistry: sodium, potassium, chloride, bicarbonate, BUN, creatinine, glucose, calcium, phosphorus, magnesium, total protein, albumin, ALT, AST, ALP, creatine kinase, LDH, total bilirubin, and uric acid. Creatinine clearance will be calculated by Cockcroft Gault equation at the screening visit, Week 1 and EOS/early termination.

k. Coagulation, and Urinalysis (Laboratory Assessments: Table 12-1). Blood draw and urine collection is prior to OBI-888 infusion. Coagulation: PT, aPPT, and INR.

Urinalysis: specific gravity, pH, protein, glucose, ketones, bilirubin, urobilinogen, blood, nitrite, leukocyte esterase as assessed by dipstick. A microscopic urinalysis (only if needed) evaluating white blood cells, red blood cells, epithelial cells, bacteria, cast and crystals

- OBI-888 is given in cycles with each individual cycle consisting of 28 days (4-week cycle). IP is administered on a weekly basis (within cycle as C1D1, C1D8, C1D15, and C1D22; C2D1, C2D8, and so on; until progressive disease, unacceptable toxicity, or decision by the Investigator or patient to discontinue treatment.
- m. Pharmacokinetic: (for analysis of serum concentration of OBI-888). Detailed schedules are provided in Table 9-2 (Part A) and Table 9-3 (Part B).
- n. Immunogenicity studies (ADA): ADA samples will be collected at the same time points, along with pre-infusion only PK samples. No post-infusion ADA samples will be collected. Detailed schedules are provided in Table 9-2 (Part A) and Table 9-3 (Part B). For subjects with persistent antibodies at end of study, an additional ADA sample will be collected at 4 months after the end of study visit.
- o. Biomarker: Detailed schedules are provided in Table 9-2 (Part A) and Table 9-3 (Part B).
- p. Radiology (CT or MRI scan) evaluations of tumor response: Performed during screening and during the study every Q8wk (±1 wk) for the first 6 months, then every Q12wk (±1 wk) thereafter. Unscheduled scans can be performed anytime, if needed to confirm disease progression. Radiology assessment for end of study follow-up and early termination should be performed unless the patient already has radiographic confirmation of progressive disease or the last exam was ≤8 weeks prior to permanent discontinuation of study drug. The same assessment method and the same technique should be used on each patient while on study.

| Table 9-2 | Part A – Pharmacokinetic | , ADA, | Biomarker | , and Gly | ycan Sam | pling | Schedule |
|-----------|--------------------------|--------|------------------|-----------|----------|-------|----------|
| | | , , | | , | | | |

| Cycle (C) | | | Сус | cle 1 | | Сус | ele 2 | Every 2 Cycles ^{e, h} | EoS / ET | |
|--|----|----------------|----------------|-------|-----|-----|----------------|-----------------------------------|----------|---------|
| Cycle Day | D1 | D2 | D4 | D8 | D15 | D22 | D1, 8, 15 | D22 | D1 | ±7 days |
| Pharmacokinetic Samples | | | | | | | | | | |
| Before infusion | Xa | | | Xb | Xb | Xb | X ^b | Xb | Xb | Х |
| End of infusion (90 minutes) ^c | Х | X ^d | X ^d | X | X | Х | Х | Х | | |
| 1 hour after end of infusion (150 minutes) ^e | Х | | | | | | | | | |
| 4 hours after end of infusion (330 minutes) ^e | Х | | | | | | | | | |
| 8 hours after end of infusion (570 minutes) ^e | Х | | | | | | | | | |
| Immunogenicity studies (ADA) ^f | Х | | | X | X | Х | Х | Х | Х | Х |
| Glycan analysis ^g | Х | | | X | X | Х | Х | Х | | |
| Biomarkers | | | | | | | | | | |
| ADCC ⁱ | Х | | | | X | | | Х | C4D1 | Х |
| CDC/ADCC ⁱ | Х | | | X | X | | | | | |
| KIR, HLA, Fc receptor gamma genotyping ⁱ | Х | | | | | | | | | Х |

ADA = antidrug antibody; ADCC = antibody-dependent cell-mediated cytotoxicity; C = cycle; CDC = complement dependent cytotoxicity; D = day; EoS/ET = End of Study/Early Termination; HLA = human leukocyte antigen; KIR = killer cell immunoglobulin-like receptor

Note: OBI-888 infusion should be administered on Days 1, 8, 15, and 22 of every 28 day cycle throughout the study treatment period.

The infusion duration of Cycle 1 and Cycle 2 are 90 minutes, and can be reduced to 30-60 minutes from Cycle 3, if there were no infusion related adverse events on prior infusions and at the discretion of the Investigator.

a. C1D1 Pre-infusion serum samples can be drawn within 1 day prior-to the infusion.

b. Pre-infusion serum samples can be collected at any time prior to the infusion on the day of the infusion.

c. Post infusion samples at the end of infusion and later (at 1, 4, and 8 hours after the end of the infusion) can be collected in a window of ± 15 minutes.

d. For Cycle1 Days 2 and 4, a single sample will be collected (window ± 2 hours):

• 24 hours after end of infusion (for infusion at C1D1)

• 72 hours after end of infusion (for infusion at C1D1)

e. If there is change of the infusion rate or interruption of infusion, the PK sampling at Day 1 are to be collected from the exact time of completion of infusion to obtain the post-infusion samples at 1, 4, 8 hour at the end of infusion. Exact time of sample collection and the reason for interruption should be documented in the eCRF.

- ADA sample will be collected along with the pre-infusion PK samples according to the above table. No post-infusion ADA samples including C1D2 and C1D4 will be collected. For subjects with persistent antibodies at end of study, an additional ADA sample will be collected at 4 months after the end of study visit.
- g. Glycan analysis: pre-infusion and end of infusion in cycle 1 and 2 only. Residual PK and ADA samples will be pooled for glycan analysis after PK and ADA data are finalized.
- h. Samples to be collected on Day 1 of C4, C6, C8, C10, C12.
- i. Biomarkers:
 - ADCC (effector cell): pre-infusion blood sample will be collected at C1D1, C1D15, C2D22, C4D1 and end of study/early termination.
 - CDC/ADCC (humoral): pre infusion and end-of-infusion blood sample will be collected at C1D1, C1D8, and C1D15.
 - KIR, HLA, Fc receptor gamma genotyping: blood sample will be collected at C1D1 (pre-infusion) and end of study/early termination.

Table 9-3 Part B – Pharmacokinetic, ADA, and Biomarker Sampling Schedule

| Cycle (C) Screening C | | | | | | | | Cycle 2 | Every 2 cycles starting with Cycle 3 ^a | Every 2 cycles starting with Cycle 4 ^c | EoS / ET |
|---|-------------------|---------------------------|------------------|----------------|----|-----|-----|---------|---|---|----------|
| Cycle Day | -28 to -1 days | D1 | D2 | D4 | D8 | D15 | D22 | D1 | D1 | D1 | ±7 days |
| Pharmacokinetic Samples | | | | | | | | | | | |
| Before infusion | | Xď | | | Xb | Xb | | Xb | | X ^b | |
| End of infusion (90 minutes) ^f | | Х | X ^{j,k} | X ^k | | Х | | | | | |
| 1 hour after end of infusion (150 minutes) ^{e,f} | | $\mathbf{X}^{\mathbf{j}}$ | | | | | | | | | |
| 3 hours after end of infusion (270 minutes) ^{e,f} | | Xj | | | | | | | | | |
| 6 hours after end of infusion (450 minutes) ^{e,f} | | Xj | | | | | | | | | |
| Immunogenicity studies (ADA) ^g | | Х | | | | | | Х | | Х | Х |
| Glycan analysis ^h | | Х | | | Х | Х | | Х | | Х | Х |
| Biomarkers | | | | | | | | | | | |
| Globo H | X ^m | | | | | | | | | | |
| ADCC/CDC (humoral) ^{d,1} | | Х | | | Х | Х | | | | | |
| KIR, HLA, Fc receptor gamma genotyping ^d | | Х | | | | | | | | | |
| Multiplex IHC ⁿ | X | | | | | | | | | | |
| Diagnostic marker ⁿ | Х | | | | | | | | | | |
| SSEA-3/SSEA-4 ⁿ | Х | | | | | | | | | | |
| Surrogate biomarker ^{d,i} | | Х | | | | | | | Х | | |

ADA = antidrug antibody; ADCC = antibody-dependent cell-mediated cytotoxicity; C = cycle; CDC = complement dependent cytotoxicity; D = day; EoS/ET = End of Study/Early Termination; HLA = human leukocyte antigen; IHC = immunohistochemistry; KIR = killer cell immunoglobulin-like receptor; SSEA = stage-specific embryonic antigens

Note: OBI-888 infusion should be administered on Days 1, 8, 15, and 22 of every 28 day cycle throughout the study treatment period.

The infusion duration of Cycle 1 and Cycle 2 are 90 minutes, and can be reduced to 30-60 minutes from Cycle 3, if there were no infusion related adverse events on prior infusions and at the discretion of the Investigator.

a. Samples to be collected on Day 1 of C3, C5, C7, C9, C11, and C13.

b. Pre-infusion serum samples can be collected at any time prior to the infusion on the day of the infusion.

c. Samples to be collected on Day 1 of C4, C6, C8, C10, and C12.

| d. | C1D1 Pre-infusion serum samples can be drawn within 1 day prior-to the infusion. |
|----|--|
| e. | If there is change of the infusion rate or interruption of infusion, the PK sampling at Day 1 are to be collected from the exact time of completion of infusion to |
| | obtain the post-infusion samples at 1, 3, 6 hour at the end of infusion. Exact time of sample collection and the reason for interruption should be documented in |
| | the eCRF. |
| f. | Post infusion samples at the end of infusion and later (at 1, 3, and 6 hours after the end of the infusion) can be collected in a window of ±15 minutes |
| g. | ADA sample will be collected along with the pre-infusion PK samples according to the above table. For subjects with persistent antibodies at end of study, an |
| | additional ADA sample will be collected at 4 months after the end of study visit. |
| h. | Glycan analysis: Residual PK and ADA samples will be pooled for glycan analysis after PK and ADA data are finalized. |
| i. | Samples should be collected to evaluate tumor-specific biomarkers (eg, CEA for colorectal, gastric, and esophageal cancer; and CA19-9 for pancreatic |
| | cancer). |
| j. | This intensive PK sampling will be collected only from first 3 patients in each cohort. |
| k. | For C1D2 and C1D4, samples can be collected in a window of ±2 hours: |
| | • 24 hours after end of infusion (for infusion at C1D1). |
| | • 72 hours after end of infusion (for infusion at C1D1). |
| 1. | Blood sample will be collected pre-infusion and end-of-infusion. |

- m. For Part B, pre-screening for Globo H tumor sample analysis may occur prior to the screening period for participation in the OBI-888-001 study.
- n. Tumor biopsy samples obtained during the initial screening visit should be used for this assessment.

10 Clinical Activity Profile Assessments

Radiology (CT or MRI scan) evaluations (± 7 days) of tumor response are to be performed during screening within 28 days prior to Cycle 1 Day 1 (first dose of study medication), and thereafter during the study every 8 weeks (Q8wk; ± 1 week) for the first 6 months, then every 12 weeks (Q12wk; ± 1 week). Unscheduled scans can be performed anytime, if needed to confirm disease progression. Radiology assessment for end of study follow-up and early termination should be performed unless the last exam was ≤ 8 weeks prior to permanent discontinuation of study drug. The same assessment method and the same technique should be used on each patient while on study.

Overall tumor response and progression will be evaluated by the Investigator according to RECIST, version 1.1.

11 Pharmacokinetics

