5.2 Study Endpoints

5.2.1 Primary Endpoints

- Dose-limiting toxicities (DLTs) with OBI-888
- AEs/SAEs and laboratory abnormalities as graded by National Cancer Institute Common Terminology Criteria for Adverse Events (NCI CTCAE) version 4.03
- MTD and RP2D of OBI-888

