6.1.3 Duration of Study

The study (Part A and B) includes a screening period (up to 28 days) prior to the first dose of OBI-888, a treatment period, and a follow-up period. Treatment will continue until progressive disease, unacceptable toxicity, or decision by the Investigator or patient to discontinue treatment.

For Part B, pre-screening for Globo H tumor sample analysis may occur prior to the screening period for participation in the OBI-888-001 study.

The safety follow-up will be conducted 28 days after the last dose of study treatment.

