12.5 Adverse Events

12.5.1 Adverse Events

An AE is any symptom, physical sign, syndrome, or disease that either emerges during the study or, if present at screening, worsens during the study, regardless of the suspected cause of the event. All medical and psychiatric conditions (except those related to the indication under study) present at screening will be documented in the medical history eCRF. Changes in these conditions and new symptoms, physical signs, syndromes, or diseases should be noted on the AE eCRF during the rest of the study. Clinically significant laboratory abnormalities should also be recorded as AEs. Surgical procedures that were planned before the patient enrolled in the study are not considered AEs if the conditions were known before study inclusion; the medical condition should be reported in the patient's medical history.

Patients will be instructed to report AEs at each study visit. All AEs are to be followed until resolution or until a stable clinical endpoint is reached.

Each AE is to be documented on the eCRF with reference to date of onset, duration, incidence, severity, relationship to study drug, action taken with study drug, treatment of event, and outcome. Furthermore, each AE is to be classified as being serious or non-serious. Changes in AEs and resolution dates are to be documented on the eCRF.

For the purpose of this study, the period of observation for collection of AEs extends from the time the patient receives the first dose of study treatment (Cycle 1 Day 1) until 28 days after end of treatment. Follow-up of the AE, even after the date of therapy discontinuation, is required if the AE persists until the event resolves or stabilizes at a level acceptable to the Investigator.

Specific guidelines for classifying AEs by intensity (Grade) and relationship to study drug are given in Table 12-2 and Table 12-3. The severity of AEs will be graded according to the NCI CTCAE version 4.03 (Grades 1 to 5).

Table 12-2 Classification of Adverse Events by Intensity (NCI CTCAE Grade)

MILD (Grade 1): An event that is easily tolerated by the patient, causing minimal discomfort, and not interfering with everyday activities.

MODERATE (Grade 2): An event that is sufficiently discomforting to interfere with normal everyday activities.

SEVERE (Grade 3): An event that prevents normal everyday activities.

LIFE-THREATENING (Grade 4)

DEATH (Grade 5)

Table 12-3 Classification of Adverse Events by Relationship to Study Drug

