12.5.3 Serious Adverse Event Reporting

An SAE occurring after receiving OBI-888 or within 28 days of stopping the treatment must be reported to the contracted contract research organization (CRO) and will be communicated to the Sponsor. Any such SAE due to any cause, whether or not related to the study drug, must be reported within 24 hours of occurrence or when the Investigator becomes aware of the event. The Investigator must send the SAE information to the Sponsor/contracted CRO using the electronic data system (preferred method), by filling out a paper SAE reporting form (to be sent via electronic mail or dedicated fax line), or by telephone line. SAEs occurring after signing of the informed consent before and before receiving OBI-888 should be reported only if the SAE was directly related to a screening procedure.

If the Investigator contacts the contracted CRO by telephone, then a written report must follow within 24 hours and is to include a full description of the event and sequelae in the AE report page of the eCRF.

The event must also be recorded on the standard AE eCRF. Preliminary reports of SAEs must be followed by detailed descriptions later on, including clear and anonymized photocopies of hospital case reports, consultant reports, autopsy reports, and other documents when requested and applicable. SAE reports must be made whether or not the Investigator considers the event to be related to the investigational drug.

Appropriate remedial measures should be taken to treat the SAE, and the response should be recorded. Clinical, laboratory, and diagnostic measures should be employed as needed in order to determine the etiology of the problem. The Investigator must report all additional follow-up evaluations to the contracted CRO within 10 calendar days. All SAEs will be followed until the Investigator and Sponsor agree the event is satisfactorily resolved.

Any SAE that is not resolved by the end of the study or upon discontinuation of the patient's participation in the study is to be followed until it either resolves, stabilizes, returns to baseline values (if a baseline value is available), or is shown to not be attributable to the study drug or procedures.

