10.7.1 PRIMARY ENDPOINTS

A. DLTs with OBI-888

The period for DLT is 28 days from the start of first dose of Investigational Product at Day 1 in study part A.

A DLT is defined as the occurrence of any of the following events within the first cycle of treatment and are considered to be at least possibly related to OBI-888:

- Grade 4 neutropenia
- Grade ≥ 3 febrile neutropenia with or without infection
- Grade 4 thrombocytopenia
- Grade ≥ 3 nausea and vomiting or diarrhea for more than 72 hours despite optimal supportive care
- Any Grade ≥ 3 non-hematological AE, except for nausea, vomiting, or diarrhea that does not resolve before the next infusion
- Grade 4 infusion reactions, and Grade ≥ 3 infusion reactions that recur despite decreasing infusion rate and optimal supportive care measures

DLTs will be displayed by assigned dose and cohort in a frequency table in decreasing order of incidence. DLTs will not be programmatically derived but analyzed as collected on the eCRF.

AE terms will be coded using the most current version of the Medical Dictionary for Regulatory Activities (MedDRA). AEs will be graded according to the NCI CTCAE version 4.03. All AEs unless they have been determined to be not related to study drug will be taken into consideration in determining DLTs.

B. AEs/SAEs and laboratory abnormalities as graded by NCI CTCAE version 4.03

A treatment-emergent adverse event (TEAE) is defined as an AE with onset dates on or after the start of study drug or if it is present prior to receipt of the study treatment but worsens in severity or increases in frequency on or after the first dose. AEs having both onset and end dates missing will be considered as TEAEs.

Events reported as "Unrelated" or "Unlikely related" to study drug will be considered as unrelated to the study drug. Events reported as "Possibly related", "Probably related", "Definitely related" to study drug or without relationship information will be considered as related to the treatment.

Tables will display the incidence of events (number of events, number of patients with any event, number of patients with any event in each specific system organ class [SOC], and number of patients with any event for each specific preferred term [PT]).

For each AE, only the highest grade and closest association with study drug by patient will be considered in the incidence analyses.

The following tables will be produced:

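### The end-of-study safety visit may be held from Day 21 after the last dose, leaving up to 7 of the 28 post-treatment days of adverse event collection with no scheduled enquiry

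*Protocol*

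**What the plan says.** AEs and SAEs are a primary endpoint. Protocol 5.2.1 lists "AEs/SAEs and laboratory abnormalities as graded by National Cancer Institute Common Terminology Criteria for Adverse Events (NCI CTCAE) version 4.03" and gives no time frame. The time frame comes from the safety sections:

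- **AE collection.** Protocol 12.5.1 sets the observation period "from the time the patient receives the first dose of study treatment (Cycle 1 Day 1) until 28 days after end of treatment".
- **SAE reporting.** Protocol 12.5.3: "An SAE occurring after receiving OBI-888 or within 28 days of stopping the treatment must be reported", whatever the cause.
- **Route of ascertainment.** Protocol 12.5.1: "Patients will be instructed to report AEs at each study visit".
- **Follow-up visit, body text.** Protocol 6.1.3: "The safety follow-up will be conducted 28 days after the last dose of study treatment". No window is given, and the synopsis agrees.
- **Follow-up visit, schedule.** The note to Protocol Table 9-1 (Section 9.2): "EoS Visit is the safety follow-up visit, conducted 28±7 days after the last OBI-888 dose". The note to SAP Table 14-1 (Appendix I) has the same window.

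On the analysis side, SAP 10.7.1 B has a treatment-emergent AE (TEAE) "defined as an AE with onset dates on or after the start of study drug", or as a pre-existing event that worsens after the first dose. Neither that definition nor the algorithm in SAP Appendix II gives an end date.

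**The concern.** The collection period ends at 28 days, but the visit meant to close it may be held a week before it ends. AEs are elicited at visits, and neither document schedules a telephone call or other contact on or after Day 28 when the visit is early. A site can follow the schedule exactly and still have no planned occasion to learn of a new event in the last days of the period.

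Safety is the primary objective, and SAP Section 3 says that the abbreviated report focuses on safety and exposure. TEAE incidence is tabulated by dose level and by cohort. Late events that nobody asks about would lower those counts, and the tables would not show it.

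**Working it through.** **Inputs.** AE and SAE period: 28 days after treatment (Protocol 12.5.1, 12.5.3). Visit target and tolerance: 28 and ±7 days after the last dose (Protocol Table 9-1 note, SAP Table 14-1 note). Half-life: 30 hours (Protocol 4.3.1).

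**Step 1: allowed visit days.** Earliest 28 − 7 = 21; latest 28 + 7 = 35.

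**Step 2: days with no scheduled enquiry.** For a visit on day *v*, and taking end of treatment to be the last dose, the uncovered part is max(0, 28 − *v*).

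| Visit day | Uncovered days | Share of 28 |
|---|---|---|
| 21 | 7 | 25.0% |
| 24 | 4 | 14.3% |
| 27 | 1 | 3.6% |
| 28 to 35 | 0 | 0% |

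**Step 3: share of the whole observation period.** Collection starts at Cycle 1 Day 1. A patient who stops after one full cycle has the last dose on Day 22, so the period is 21 + 28 = 49 days and the largest loss is 7/49 = 14.3%. After two full cycles it is 49 + 28 = 77 days and 7/77 = 9.1%. The share falls further with longer treatment.

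**Step 4: chance that an onset falls in the gap.** The documents give no late event rate, so this is an assumed range. Let *p* be the chance of at least one new AE in the 28 days, with constant hazard. For a patient seen on Day 21, the chance of an onset in the last 7 days is 1 − (1 − *p*)^(7/28).

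| *p* | Onset in the uncovered 7 days |
|---|---|
| 5% | 1.3% |
| 10% | 2.6% |
| 20% | 5.4% |
| 30% | 8.5% |

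These are chances of an onset, for the earliest permitted visit. The chance of a missed event is lower, because some onsets would reach the site anyway.

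**Step 5: drug remaining.** Day 21 is 21 × 24 / 30 = 16.8 half-lives after the last dose, and 2^(−16.8) is about 0.0009%. Day 28 is 22.4 half-lives.

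**Step 6: does another provision close the gap?**
- Continued follow-up in 12.5.1 concerns AEs that persist, not new onsets.
- Unscheduled assessments (9.2) are at the investigator's discretion.
- The 4-month contact is an antibody sample, only for patients with persistent antibodies.
- The early termination visit (7.3) is not tied to Day 28.
- The SAE duty in 12.5.3 runs to Day 28 but creates no contact.

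None of these requires an enquiry on or after Day 28.

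**Step 7: anchor dates.** Sections 12.5.1 and 12.5.3 count from the end or stopping of treatment; the visit is counted from the last dose. If end of treatment were dated *k* days after the last dose, the largest gap would be 7 + *k* days.

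**The case against.** The strongest reply is that an early visit ends scheduled contact, not the observation period. That stands. An SAE within 28 days of stopping must still be reported within 24 hours of occurrence or awareness, and any AE in the period that comes to light is still to be recorded. The exposure is therefore mainly to new non-serious events that a patient would mention only if asked. The protocol's body text also aims at Day 28 itself, and at the reported half-life few drug-related events are likely to be lost. Against this, the tables count TEAEs of any cause, and delayed immune effects cannot be judged from these documents.

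A reader might infer three stronger things that the documents do not support:

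- **That nearly half of patients cannot be observed to Day 28.** If visits were spread evenly over Days 21 to 35, 7 of 15 days (46.7%) would precede Day 28. But any distribution symmetric about Day 28 puts just under half of visits before it, so the figure only restates the assumption. The documents hold no data on visit timing.
- **That follow-up runs from 21 to 35 days and late events enter the tables.** Section 12.5.1 ends AE collection at 28 days. A visit on Days 29 to 35 covers the whole period; it does not extend it. The TEAE definition without an end date matters only if a site records events that the protocol does not ask for.
- **That comparisons across doses or cohorts are biased.** Nothing suggests that visit timing differs between groups. Summaries are descriptive, and treatment until progression can create much larger differences in follow-up.

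**Conclusion.** The inconsistency is real and small. The schedule permits a final safety visit up to 7 days before AE and SAE collection closes, and no passage requires a contact on or after Day 28 when that happens. The consequence is possible modest under-ascertainment of new late events, mainly non-serious ones. The bound of 7 of 28 days (25%) for one patient follows from the text, provided that end of treatment means the last dose; the number of patients affected and of events missed does not. Dose-limiting toxicities are untouched, because their 28 days run from the start of treatment (Protocol 6.2). The severity is minor; the point is worth making because the remedy is cheap.

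**What to change.** 1. In the note to Protocol Table 9-1 and the matching note to SAP Table 14-1, change the end-of-study window to 28 days, +7 days (Days 28 to 35 after the last dose). Alternatively, keep ±7 days and require a documented AE/SAE enquiry on or after Day 28 for anyone seen earlier; a telephone call is enough. Either change reduces the largest uncovered interval from 7 days to 0.
2. Reconcile Protocol 6.1.3, 12.5.1, 12.5.3 and the Table 9-1 note so that all use one anchor date, and state whether end of treatment means the date of the last dose.
3. Optionally, as a safeguard, state in SAP 10.7.1 B that the TEAE period ends at last dose + 28 days, to match Protocol 12.5.1.

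The cost is a few lines of text and either slightly less scheduling freedom or a short call. SAP version 2.0 describes conduct largely in the past tense, so item 1 helps only patients still to be followed; item 3 can be adopted in the analysis at any time before the tables are produced.
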